#### 12.1.5.5. Samples for Reanalysis or Future Assessments

Any biological specimens remaining at the end of the study may be used for re-assay, future assay development and validation, or for future exploratory analyses to improve the understanding of vLINCL6 disease and its management.

Additionally, for subjects who consent, additional biological sample collection for safety, efficacy, or other research assessments may also be performed at each annual visit. Biological samples collected may include blood, saliva, stool, urine, and/or CSF.

Lumbar puncture will be performed on Day 0 for administration of AT-GTX-501 and collection of CSF. Any additional CSF collection at Month 24 will be as per the consent documents/text related to anesthesia, as anesthesia is required for the lumbar puncture. The potential additional CSF collection at Month 24 would occur following any other EUAs (described in Section 11.9).

## 12.2. Adverse and Serious Adverse Events

The investigator and study personnel are responsible for detecting, documenting, and reporting AEs and SAEs. For each subject, reporting of AEs and SAEs is to begin after written informed consent is provided. Through the Month 24 visit, all AEs will be followed until resolution or stabilization. Any AEs ongoing at the conclusion of the study that are not considered related to AT-GTX-501 will not be followed after the subject completes the Month 24 visit.

Throughout the study, opportunities to report AEs will be provided. The definitions of AE and SAE are in Section 12.2.1.1 and Section 12.2.1.2, respectively. Reporting instructions for AEs and SAEs are in Section 12.5.1 and Section 12.5.2, respectively.

If needed to determine appropriate treatment or the causality of AEs/SAEs, appropriate follow-up procedures will be conducted.

## 12.2.1. Definition of Adverse Events

#### 12.2.1.1. Adverse Event

An AE is defined as any untoward medical occurrence in a subject administered a pharmaceutical product, biologic, or medical device (medicinal products). The AE does not necessarily have a causal relationship with the medicinal product. An AE can therefore be any unfavorable and unintended sign, symptom, or disease temporally associated with the use of a medicinal product, whether or not considered related to the medicinal product. Adverse events may include the onset of new illness and the exacerbation of pre-existing conditions.

Therefore, AEs may include:

- New signs, symptoms, conditions, or illnesses
- Exacerbation (eg, increase in intensity, frequency) of pre-existing signs, symptoms, conditions, or illnesses after subjects provide informed consent
- AEs related to a protocol-required procedure
- Abnormal laboratory findings deemed clinically significant by the investigator

- Physical or neurological examination changes deemed clinically significant by the investigator
- Other abnormal medical findings (eg, ECG) that were not documented at Visit 1 and/or, in the investigator's opinion, represent a clinically significant change in the subject's health during study participation
  - Medical findings at Visit 1 (eg, ECG) that were not previously provided as medical history but can be determined as starting prior to Visit 1 are not considered AEs and are to be recorded as medical history

#### 12.2.1.2. Serious Adverse Event

An SAE is an AE occurring during any study phase (eg, baseline, treatment, or follow-up) that fulfils any of the following:

- Results in death
- It is life-threatening (places the subject at immediate risk of death)
  - As assessed by either the investigator or Amicus
  - This does not include an AE that, had it occurred in a more serious form, hypothetically might have caused death.
- It requires inpatient hospitalization or prolongs existing hospitalization
  - Emergency room/department or outpatient treatments that do not result in admission do not have to be reported as an SAE, unless another SAE criterion is met.
    - Events assessed and treated in these circumstances are to be captured as AEs.
  - Hospitalizations for elective or pre-planned treatment of a pre-existing condition do not have to be reported as SAEs provided the condition is documented in the subject's source documents and has not worsened since written informed consent was first completed
  - Hospitalization signifies the subject has been admitted, regardless of duration, for observation and/or treatment that would not have been appropriate in a physician's office or outpatient setting.
  - Hospitalizations solely based on logistics (eg, subject is admitted due to limited hospital accessibility for what would otherwise be an outpatient procedure) do not have to be reported as SAEs, provided they are clearly defined as such in the subject's source record.
- It results in persistent or significant incapacity or substantial disruption of the ability to conduct normal life functions
- It results in a congenital anomaly/birth defect

An important medical event that may not result in any of the above serious outcomes may be considered an SAE when, based upon appropriate medical judgment, it may jeopardize the

subject and may require medical or surgical intervention to prevent any of the above serious outcomes. Examples of such medical events include allergic bronchospasm requiring intensive treatment in an emergency room or at home, blood dyscrasias, convulsions that do not result in inpatient hospitalization, or development of drug dependency or drug abuse.

If the following 4 elements are known regarding an SAE, the event must be reported as described in Section 12.5.2:

- Identifiable subject
- AE term
- Study treatment, AT-GTX-501
- Identifiable reporter

Additionally, the investigator's assessment of an event's relationship to AT-GTX-501 (see Section 12.3) is essential for Amicus to appropriately process the report and is to be included.

Subjects are to be informed that they are to report events meeting the definition of seriousness to study personnel as soon as possible (and to not wait until their next study visit). If a non-serious AE becomes an SAE, the change in status is to be appropriately entered in the case report form (CRF) and the subject's source record, and reported to Amicus as described in Section 12.5.2.

#### 12.2.1.3. Expected Events Related to Disease Progression

Subjects enrolled in this clinical protocol are expected to present clinically with events related to natural progression of the disease.

Any AEs determined to be due to the underlying disease progression may not be subject to the expedited reporting requirements outlined in Section 12.5.3. Changes in these disease symptoms are to be reviewed by the investigator or a medically qualified sub-investigator. Expected or anticipated changes in these clinical conditions may not qualify as AEs. However, if there is a clinically relevant worsening of a sign or symptom of the disease under treatment and the outcome fulfills the definition of an AE, it is to be reported.

Anticipated vLINCL6 disease-related signs and symptoms related to progression of the disease are:

- Impaired motor function
- Impaired speech
- Impaired cognitive function
- Movement disorder
- Seizures
- Hallucinations

- Sleep abnormalities
- Behavioral difficulties
- Blindness
- Irritability
- Dementia

## 12.2.1.4. Anticipated Adverse Events of Laboratory Findings Related to Intervention

Following gene transfer, elevation of transaminases (levels up to 5X the upper limit of normal [ULN]) with preserved liver synthetic function and no significant elevation in GGT are anticipated and will be recorded as AEs and graded per CTCAE guidelines. Mild decreases in leukocyte and lymphocyte counts within the first 30 days after gene transfer have been observed in other studies of AAV-mediated gene transfer. Such transient decreases in lymphocytes or leukocytes will be recorded as AEs but considered anticipated.

Leukocytosis and neutrophilia during prednisone or prednisolone treatment:

An elevation of up to 5000 cells/mm^3 above the subject's baseline value is expected in the neutrophil count (the primary granulocyte in circulation) and, consequently, in the leukocyte count within 5 hours of initiating prednisone or prednisolone therapy, based upon studies in healthy adult volunteers. This occurs secondary to release of granulocytes from the marginated pool into the circulation accompanied by an increase in the size of the marginated granulocyte pool due to steroids (Munroe, Mitchison et al. 1997; Cotman, Vrbanac et al. 2002). This steroid effect may be seen with increased steroid dosing.

#### 12.2.1.5. Dose-limiting Toxicity

A DLT is defined as any unanticipated AE that is related to AT-GTX-501 (events assessed by the investigator as definitely, probably, or possibly related) and is Grade 3 or higher, according to the CTCAE version 4.0 (published 28 May 2009). See Section 12.4.1 for further description of the CTCAE grades.

# **12.3.** Relationship to Study Treatment

The investigator or a medically qualified sub-investigator will review each AE and assess its relationship to AT-GTX-501 based on available information and according to the following guidelines:

- **Definite (1)**: A reaction that follows a distinct temporal relationship from administration of the study treatment that follows a known reaction to the agent or chemical group of the study treatment; and that cannot be explained by the subject's clinical state or other factors
- **Probable (2)**: A reaction that follows a reasonable temporal sequence from administration of the study treatment; that follows a known or expected response pattern to the suspected study treatment; and that could not be reasonably explained by the known characteristics of that subject's clinical state
- **Possible (3)**: A reaction that follows a reasonable temporal sequence from administration of the study treatment; that follows a known or expected response pattern to the suspected study treatment; but that could readily have been produced by a number of other factors
- Unlikely (4): A reaction that does not follow a reasonable temporal sequence from administration of study treatment. However, causality from the medication cannot be excluded

• Unrelated (5): A reaction for which sufficient data exist to indicate that the etiology is unrelated to the study treatment

For the purpose of the definition of DLTs (as defined in Section 12.2.1.5) and expedited SAE regulatory reporting obligations (ie, to regulatory authorities and the Institutional Review Board [IRB]), events assessed by the investigator as definitely, probably, or possibly related to AT-GTX-501 will be considered "related" to AT-GTX-501. Events assessed as unlikely or unrelated will be considered "not related" to AT-GTX-501.

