#### 5.3.2. Rationale for Study Treatment

This is the first clinical study of AT-GTX-501. The target for this gene transfer study is vLINCL6 disease. The *CLN6* gene will be transferred using scAAV9 carrying the human *CLN6* gene under control of a hybrid cytomegalovirus enhancer/chicken-β-actin promoter (AT-GTX-501). The specific scAAV9 viral vector was chosen based on both nonclinical studies and its safety in human subjects as seen in a Phase I clinical study for infants with type I spinal muscular atrophy (Mendell, Al-Zaidy et al. 2017).

The rationale for this approach is based on studies of the natural history of vLINCL6 disease, its genetic cause, and its lack of therapies.

Pathogenic mutations in the *CLN6* gene cause vLINCL6 disease, which is a severe neurodegenerative disorder leading to dementia, epilepsy, motor impairment, and visual loss. The age of disease onset varies between 18 months and 8 years, but the outcome is fatal in all cases, typically leading to death within the first 15 years of life. The CLN6 protein is a transmembrane protein located in the endoplasmic reticulum (Gao, Boustany et al. 2002). As with many other Batten disease-causing gene products, the exact function of the CLN6 protein is still unknown. This makes it difficult to develop effective drug-based therapies for this devastating disorder, as the affected pathways that need to be targeted are poorly understood. Moreover, the ubiquitous expression of the CLN6 protein and the sensitivity of various neuronal cell types to its malfunction requires widespread targeting of treatment throughout the CNS and potentially other organs of the body. The pathogenic *CLN6* mutations described to date are thought to cause a reduced abundance or functionality of the protein (Heine, Koch et al. 2004). Therefore, strategies aiming to restore CLN6 protein expression and/or function are under investigation as therapeutic approaches. Current treatments are only palliative in nature and no therapies exist to treat the underlying cause of vLINCL6 disease.

Preceding nonclinical and clinical safety studies have shown scAAV9-mediated gene transfer to be safe and well-tolerated in mice, cats, monkeys, and in human subjects in clinical studies (Foust, Salazar et al. 2013; Bucher, Dubreil et al. 2014; Meyer, Ferraiuolo et al. 2015; Mendell, Al-Zaidy et al. 2017).

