### 6.1. **Primary Objective**

The primary outcome for this clinical study is safety. This is evaluated based on an outcome measure of dose-limiting toxicity (DLT), defined in Section 12.2.1.5 as any unanticipated AE that is related to AT-GTX-501 (events assessed by the investigator as definitely, probably, or possibly related) and is Grade 3 or higher, according to the Common Terminology Criteria for Adverse Events (CTCAE) version 4.0 (published 28 May 2009).

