#### 12.5.3. Additional Reporting Requirements for Suspected Unexpected Serious Adverse Reactions

Any AE that is serious, unexpected, and associated with the use of study treatment has additional reporting requirements. For each SAE, Amicus will determine the expectedness of AEs according to current safety reference document.

Amicus is responsible for processing suspected unexpected serious adverse reactions (SUSARs). These SUSAR reports are also referred to as alert reports, expedited safety reports, and investigational new drug (IND) safety reports. A SUSAR is defined as any SAE that is determined to be associated with the use of the study treatment and is unexpected (not currently listed in the current safety reference document, as described in Section 12.2.1.3, or is not listed at the specificity or severity that has been observed).

Amicus will ensure SUSARs are reported to the FDA, in accordance with local laws.

- If the SUSAR is fatal or life-threatening, regulatory authorities and ethics committees are to be notified within 7 calendar days after Amicus learns of the event.
- If the SUSAR is not fatal or life-threatening, regulatory authorities and ethics committees are to be notified within 15 calendar days after Amicus learns of the event.

Additionally, safety updates will be provided periodically to the FDA and the relevant IRB. These updates will include information on SUSARs as well as other relevant safety findings.

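### Section 12.3 requires a known or expected pattern for every related category, so a novel Grade 3 or higher event can enter the DLT count only if the investigator departs from the written guideline

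*Protocol*

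**What the plan says.** Protocol Section 12.3 asks the investigator or a medically qualified sub-investigator to rate each AE "based on available information and according to the following guidelines". The five categories, in substance, are:

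- **Definite:** distinct timing, a known reaction to the agent or its class, and no explanation from clinical state or other factors.
- **Probable:** reasonable timing, a known or expected pattern, and no reasonable explanation from the subject's clinical state.
- **Possible:** reasonable timing and a reaction "that follows a known or expected response pattern to the suspected study treatment; but that could readily have been produced" by other factors.
- **Unlikely:** "A reaction that does not follow a reasonable temporal sequence from administration of study treatment", although causality cannot be ruled out.
- **Unrelated:** adequate evidence that the cause lies elsewhere.

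The first three count as related and the last two do not, both for DLTs and for expedited SAE reporting.

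Section 12.2.1.5 states: "A DLT is defined as any unanticipated AE that is related to AT-GTX-501", adding that it must be rated definite, probable or possible and be Grade 3 or higher. Section 6.1 makes the DLT the measure of the primary outcome, safety. Section 5.3.2 states: "This is the first clinical study of AT-GTX-501". Section 12.5.3 allows a SUSAR to be an event "not currently listed in the current safety reference document" that is nevertheless associated with treatment.

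**The concern.** A DLT has to be unanticipated, and a SUSAR may be absent from the reference document altogether. The protocol therefore foresees treatment-related events that nobody predicted. Section 12.3, however, makes conformity with something known or expected a condition of every related category. For an event outside any such pattern the guideline offers no related descriptor. The only category that speaks of causality not being excluded is Unlikely, which counts as not related, so the wording pulls such an event out of the DLT count.

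The same rating drives several other things:

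- the two DLT-based enrollment pause triggers in Section 7.5;
- related status for expedited reporting (Section 12.3);
- follow-up, since under Section 12.2 ongoing AEs "that are not considered related to AT-GTX-501 will not be followed after the subject completes the Month 24 visit";
- the tables by relationship in Sections 13.2.4.1.1 and 13.2.4.1.2.

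Because the guideline gives no answer for a novel event, two raters could classify the same event differently and both claim to have followed the protocol.

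**Working it through.** **Test case.** Take a Grade 3 or higher AE with reasonable timing, no known or expected pattern, and no evidence establishing another cause. Against each descriptor in Section 12.3:

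- Definite fails: no known reaction.
- Probable fails: no known or expected pattern.
- Possible fails for the same reason.
- Unlikely fails: the timing is reasonable.
- Unrelated fails: another cause has not been shown.

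The event meets 0 of 5 definitions and 0 of the 3 related ones. The conditions are cumulative, joined by *and* or *but*. The note in Section 12.4.1 that a semi-colon means *or* applies only to the CTCAE grade descriptions.

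**Enumeration.** Timing (reasonable or not) × pattern (known/expected or not) × other cause (no other explanation, other factors could explain, other etiology shown) gives 2 × 2 × 3 = 12 combinations.

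| Timing | Pattern | Other cause | Cells | Category |
|---|---|---|---|---|
| either | either | other etiology shown | 4 | Unrelated |
| not reasonable | either | not shown | 4 | Unlikely |
| reasonable | known/expected | no other explanation | 1 | Definite or Probable |
| reasonable | known/expected | other factors could explain | 1 | Possible |
| reasonable | none | no other explanation | 1 | none |
| reasonable | none | other factors could explain | 1 | none |

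Totals: 4 Unrelated + 4 Unlikely + 2 related + 2 without a category = 12. Both uncovered cells have reasonable timing and no known pattern, and in one of them nothing else explains the event.

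The third axis simplifies, because Definite, Probable and Possible each word the other-cause test a little differently. This does not affect the two uncovered cells: there the related categories fail on pattern and Unlikely fails on timing.

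**Effect of two repairs.**

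- Deleting only the pattern clause from Possible leaves 1 cell uncovered (reasonable timing, no pattern, no other explanation), because Possible also requires that other factors could readily have caused the event.
- Wording Possible as reasonable timing with causality not excluded leaves 0 cells uncovered.

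**Illustration of the stakes.** Section 7.2 plans about 13 subjects. Clopper-Pearson 95% intervals for n = 13:

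- 0/13: upper limit 1 − 0.025^(1/13) = 0.247, so 0% (0 to 24.7%).
- 1/13 = 7.7%: lower limit 1 − 0.975^(1/13) = 0.002; the upper limit solves (1 − p)^13 + 13p(1 − p)^12 = 0.025, giving p = 0.360. So 7.7% (0.2 to 36.0%).

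Under Section 7.5, one Grade 4 event, or Grade 3 events in two subjects, would decide whether a DLT pause trigger is met.

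**The case against.** The strongest reply is that the operative rule is the investigator's assessment. The descriptors are guidelines, and nothing sends an uncovered event to a not-related category. An investigator who judges a novel event possibly related can say so, and it then counts. That is correct, but it requires departing from the descriptor, and a primary-outcome count should not rest on that.

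A second reply is that *expected* can be read as plausible for this type of product, and that the protocol's terms unanticipated, unexpected and expected pattern refer to different things. This also stands in part. DLTs and SUSARs remain possible as written: a transaminase rise beyond the level that Section 12.2.1.4 calls anticipated, or a host immune response of the kind described in Section 9.1.1, still fits. The gap is confined to events outside any known or expected pattern, and a broad reading narrows it further.

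Third, other provisions soften the safety consequence:

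- pause triggers that need no DLT rating, and DSMB discretion (Section 7.5);
- ad hoc DSMB meetings (Section 14.4.2);
- 24-hour reporting of all SAEs (Section 12.5.2);
- TEAE tables by grade (Section 13.2.4.1.1) and by-subject listings (Section 13.2.1);
- the long-term study for those who transfer (Section 9.6).

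Dosing of the first 12 subjects is described in the past tense (Section 7.6), so the effect on pausing is mostly over. All true, but none of these puts the event into the DLT count.

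Finally, there is one center, which limits variation between raters, though sub-investigators may also rate. The cell count is not a frequency, and the 0/13 and 1/13 intervals would apply to any single reclassified event. Both are offered only as logic and scale.

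**Conclusion.** The concern holds and should be fixed. Read as written, Section 12.3 leaves 2 of 12 combinations without a category, both of them plausibly timed novel events. Such an event counts toward the primary outcome only if the rater sets the pattern condition aside. Each one rated differently changes the DLT count by one subject if that subject has no other DLT, which is 7.7 percentage points at n = 13. This rests on a literal reading of cumulative conditions and on the planned sample of about 13. It does not show that DLTs are impossible, or that any event was in fact misclassified.

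**What to change.** Reconcile Section 12.3 with Section 12.2.1.5. Treat a known or expected pattern as evidence that strengthens the rating, not as a required condition, at least for Possible. Word Possible so that an event with reasonable timing whose causality cannot be excluded may be rated Possible, whether or not other factors could also explain it, and so counts as related. Removing the pattern clause alone is not enough.

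Keep the ratings already recorded. Any re-assessment under the corrected wording is optional and should be shown only beside them, so that ratings made under the two wordings are not mixed in one count.

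The text change is one definition in one section, but it is not administrative, so Section 16.3.1 requires a formal amendment with the usual approvals. The downside is that somewhat more events will count as related.

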# **12.4.** Recording Adverse Events

For each subject, reporting of AEs begins after written informed consent is completed. Adverse events may be volunteered spontaneously by the subject or discovered as a result of general, non-leading questioning by or observation by study personnel.

Adverse events will be recorded in the CRF and subject's source record beginning from the time written informed consent is completed through the end of this study. The AE term is to be reported in standard medical terminology when possible. A single diagnosis is to be entered when known. If a clear diagnosis cannot be determined at the time of CRF and the subject's source record entry, each sign and symptom is to be recorded individually until a final diagnosis is established.

For each AE, the following is to be recorded:

- Date and, as possible, time the AE started and ended
- Action(s) taken with study treatment
- Outcome (resolved, resolved with sequelae, ongoing, or fatal)
- Intensity (see Section 12.4.1)
- Relationship to AT-GTX-501 (see Section 12.3)

Additional required information may be detailed in CRF completion guidelines.

All conditions (including those that are considered related to vLINCL6 disease), signs, or symptoms that are reported as part of the subject's medical history are only to be reported as AEs if they worsen (ie, increase in intensity) following the completion of Visit 1. If a nonserious AE becomes serious, the SAE must be reported as described in Section 12.5.2.

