#### 12.4.1. Assessment of Adverse Event Intensity

When the determination of AE intensity rests on medical judgment, the determination of intensity must be made with the appropriate involvement of the investigator or a qualified sub-investigator.

The definitions/classification for rating intensity will follow the guidelines outlined in CTCAE version 4.0 (published 28 May 2009), which includes:

• Grade 1 Mild; asymptomatic or mild symptoms; clinical or diagnostic observations only; intervention not indicated

- Grade 2 Moderate; minimal, local, or noninvasive intervention indicated; limiting age-appropriate instrumental activities of daily living
- **Grade 3** Severe or medically significant but not immediately life-threatening; hospitalization or prolongation of hospitalization indicated; disabling; limiting self-care activities of daily living
- Grade 4 Life-threatening consequences; urgent intervention indicated
- Grade 5 Death related to AE

Note: A semi-colon indicates 'or' within the description of the grade.

Note: Instrumental activities of daily living refer to preparing meals, shopping for groceries or clothes, using the telephone, managing money, etc.

Note: Self-care activities of daily living refer to bathing, dressing and undressing, feeding self, using the toilet, taking medications, and not bedridden.

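### Section 12.4 records worsening of medical-history conditions as AEs only if intensity rises after Visit 1, while the AE definition in Section 12.2.1.1 also names frequency and starts at informed consent

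*Protocol*

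**What the plan says.** Section 12.4 sets the recording rule. It covers "All conditions (including those that are considered related to vLINCL6 disease), signs, or symptoms" that form part of the medical history, and says that they "are only to be reported as AEs if they worsen (ie, increase in intensity) following the completion of Visit 1". The same section starts AE recording in general at written informed consent.

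Section 12.2.1.1 defines the AE. Its list of what AEs may include has the item "Exacerbation (eg, increase in intensity, frequency) of pre-existing signs, symptoms, conditions, or illnesses after subjects provide informed consent".

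Section 12.2.1.3 deals with disease progression. It first allows discretion: "Expected or anticipated changes in these clinical conditions may not qualify as AEs". It then requires a report where there is "clinically relevant worsening of a sign or symptom of the disease under treatment and the outcome fulfills the definition of an AE". Seizures, hallucinations, sleep abnormalities, behavioral difficulties and irritability are among the 11 signs it lists as anticipated.

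Two related wordings stand in Section 8.4. It treats illnesses present at Visit 1 as AEs, and it labels any concomitant illness that emerges or worsens in the course of the study a TEAE. Section 13.2.4.1 reserves TEAE for AEs after receipt of AT-GTX-501. Section 12.2.1.1 sends Visit 1 findings that began earlier to medical history.

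**The concern.** Section 12.4 uses *only* and glosses worsening with *ie*, so intensity is the sole criterion. The definition it should apply gives intensity and frequency as examples. A site that follows Section 12.4 to the letter will not enter an event that the protocol's own definition admits.

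What depends on this is the completeness of the AE record. The TEAE tables by intensity and relationship (Section 13.2.4.1.1) and the per-participant AE totals in the DSMB reports (Section 14.4.2) contain only what was entered as an AE. An SAP can choose how to tabulate recorded AEs, but it cannot add ones that sites were told not to record. In a disease where episodic symptoms such as seizures are often present at entry, more frequent episodes are a natural form of worsening.

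**Working it through.** The main check compares passages. The only arithmetic concerns dates and scale.

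**1. The rules side by side**

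| | Section 12.4 | Section 12.2.1.1 | Section 12.2.1.3 |
|---|---|---|---|
| Criterion | Intensity only | Intensity or frequency, as examples | Clinically relevant worsening that meets the AE definition |
| Start | Completion of Visit 1 | Informed consent | Not stated; follows the definition |
| Force | Exclusive | Permissive list | Mandatory once the definition is met |

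Section 12.2.1.3 has no criterion of its own and points back to the AE definition. There is therefore one underlying mismatch, between Section 12.4 and the definition.

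**2. A test case.** Take a child with seizures in the medical history whose seizures become more frequent after dosing, at the same CTCAE grade and with no seriousness criterion met.
- Section 12.2.1.1: can be an AE (exacerbation by frequency).
- Section 12.2.1.3: to be reported if the investigator judges the worsening clinically relevant and the definition met.
- Section 12.4: not to be reported, because intensity has not risen.

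The instructions cannot all be followed.

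**3. What escapes.** The gap is limited to non-serious, same-grade, frequency-only worsening. Other routes catch more marked changes:
- On grading, "The definitions/classification for rating intensity will follow the guidelines outlined in CTCAE version 4.0". Under the generic grades in Section 12.4.1, a rise that calls for intervention or limits daily living can change the grade.
- Section 12.2.1.1 also lists "Physical or neurological examination changes deemed clinically significant by the investigator" as possible AEs.
- Section 12.2.1.2 gives "convulsions that do not result in inpatient hospitalization" as an example of a possible SAE, and Section 12.4.2 requires SAE reporting at any intensity.

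**4. Effect on DLTs.** Sections 6.1 and 12.2.1.5 require an AE that is unanticipated, related and Grade 3 or higher. A condition that moves from a lower grade to Grade 3 has increased in intensity, so Section 12.4 captures it. The disease symptoms listed in Section 12.2.1.3 are anticipated in any case. What remains is an unlisted condition already at Grade 3 or higher at entry that worsens in frequency alone.

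**5. Start point.** If consent and Visit 1 both fall in the screening window of Day -30 to Day -2 (Table 3), the two start points differ by at most 30 - 2 = 28 days. All of these precede Day 0, so no TEAE count changes.

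**6. Section 8.4.** Its TEAE wording differs from Section 13.2.4.1 only between consent and dosing, which is 2 to 30 days per subject on the same assumption. AE start dates resolve it. Illnesses present at Visit 1 are pre-dose and can affect all-AE summaries only. Section 7.6 describes dosing of the initial 12 of about 13 subjects in the past tense (12/13 = 92%). The synopsis estimates last completion in the fourth quarter of 2021 with 2 years per subject, which puts last dosing at about the fourth quarter of 2019. Few or no subjects were therefore likely to be still pre-dose, although Section 7.6 does not settle this.

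**7. Scale.** With 13 subjects, one subject is 1/13 = 7.7% in an incidence table. That is the step size of the table. It is not an estimate of how many events are missed.

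**The case against.** The best case for leaving the text alone has four parts.

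- **The definition is permissive.** Section 12.2.1.1 says what AEs may include, and Section 12.2.1.3 lets anticipated changes fall outside AE status. This stands as a softening. It does not remove the conflict, because a definition that admits frequency cannot be applied through a recording rule that excludes it.
- **CTCAE grading may already count frequency.** The protocol reproduces only the generic grades, so how often more frequent seizures would change the grade cannot be settled from the document. This stands, and it is one reason why no size is claimed.
- **The information is not lost.** The UBDRS collects seizure and behavioural data at screening, Day 30 and every 3 months from Month 3 (Section 11.2). The Hamburg scale was designed to collect grand mal seizure incidence (Section 11.1), long-term EEGs capture clinical seizures (Section 11.4), and medication changes are recorded with reasons (Section 12.1.2). This largely stands. A reader might infer that worsening seizures would disappear from the study data, and the protocol does not support that. What these sources lack is the AE grade and the relatedness assessment.
- **The primary outcome is DLT.** A reader might infer that, because safety is the primary outcome, the primary result is at risk. The protocol does not support that either: the outcome is judged on related, unanticipated events of Grade 3 or higher, and a rise to that grade meets the Section 12.4 test.

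**Conclusion.** The inconsistency is real and should be corrected. As written, Section 12.4 drops events that the AE definition admits: non-serious worsening by frequency alone, at an unchanged grade, of conditions in the medical history. The AE and TEAE tables and the AE totals sent to the DSMB would be incomplete to that extent.

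The consequence is narrow. The DLT outcome is essentially unaffected, and seizure and behaviour changes can still be seen in other study data. The documents give no rate of frequency-only worsening, so no count or percentage of missed events can be stated. The conclusion assumes that sites follow Section 12.4 literally; sites that work from Section 12.2.1.1 would already record these events.

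A reader might also infer that Section 12.4 breaks two independent rules. It does not, since Section 12.2.1.3 only refers back to the definition. The Section 8.4 differences are matters of consistency, and neither changes TEAE counts once AE start dates are applied.

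**What to change.** Reconcile Section 12.4 with Section 12.2.1.1: one worsening criterion (an increase in intensity or frequency) and one start point (informed consent). Keep the investigator's judgement of clinical relevance in Section 12.2.1.3, so that expected progression is not recorded automatically. Carry the same wording into the CRF completion guidelines. State the date of the change in the study report, because AE ascertainment may differ before and after it.

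For consistency only, reword Section 8.4 so that TEAE status follows Section 13.2.4.1 (after receipt of AT-GTX-501), and so that conditions that began before Visit 1 go to medical history, as in Section 12.2.1.1.

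The cost is a wording amendment and slightly more AEs recorded. The change acts prospectively. With at least 12 of about 13 subjects already dosed, it affects only their remaining follow-up and does not recover events left out earlier.
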